4.6.2.3 Vital Signs

The baseline value will be the last non-missing value taken prior to first dose of study drug.

Vital signs (systolic blood pressure [SBP], diastolic blood pressure [DBP], temperature, and heart rate) will be summarized using mean, standard deviation, minimum, maximum and median by treatment group and visit. Additionally, a within-participant change will be calculated per visit as the post-baseline measurement minus the baseline measurement and summarized by treatment group and overall at each visit.

A separate table will be provided to summarize respiration rate for participants off ventilator using mean, standard deviation, minimum, maximum and median by treatment group, age group, and visit.

Tables for potentially clinically significant vital signs will be generated using baseline value and highest/ lowest value obtained during treatment for each participant for each treatment group.

The following potentially clinically significant criteria are defined for each parameter:

Table 6 Potentially Clinically Significant Criteria for Vital Signs

Vital Sign Variable	Age Group	Criteria (Low)	Criteria (High)
SBP	1 – 12 Months	< 72 mmHg	>104
	1 – 2 Years	< 86 mmHg	>106 mmHg
	3 – 5 Years	< 89 mmHg	>112 mmHg
	6 – 7 Years	< 97 mmHg	>115 mmHg
	≥ 8 Years	< 102 mmHg	>131 mmHg
DBP	1 – 12 Months	< 37	>56
	1 – 2 Years	< 42 mmHg	>63 mmHg
	3 – 5 Years	< 46 mmHg	>72 mmHg
	6 – 7 Years	< 57 mmHg	>76 mmHg
	≥ 8 Years	< 64 mmHg	>83 mmHg
HR	1 – 12 Months	< 111 bpm	>182 bpm
	1 – 2 Years	< 108 bpm	>180 bpm
	3 – 5 Years	< 88 bpm	>152 bpm
	6 – 7 Years	< 75 bpm	>118 bpm
	≥ 8 Years	< 60 bpm	>100 bpm
RR	1 – 12 Months	< 27 bpm	>45 bpm
	1 – 2 Years	< 21 bpm	>43 bpm
	3 – 5 Years	< 18 bpm	>31 bpm
	6 – 7 Years	< 17 bpm	>25 bpm
	≥ 8 Years	< 12 bpm	>22 bpm

BL = baseline, SBP = systolic blood pressure, DBP = diastolic blood pressure, HR = heart rate, RR = respiratory rate

All vital signs parameters will be listed. The listing will flag any vital signs that exceed the levels provided in the table above.

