Following the occurrence of fatal serious AEs (SAEs) in Study ATX-MTM-002, the Sponsor, in consultation with the DMC and external experts, evaluated the data and reassessed the benefit/risk profiles of the 1.0×10^{14} vg/kg and 3.0×10^{14} vg/kg dose levels. As of the data cutoff date of 08 July 2020, 5 subjects who received 3.0×10^{14} vg/kg AT132 developed AT132-related SAEs involving the hepatobiliary system. In 2 subjects, these SAEs resolved; in 3 subjects, fatal events occurred subsequent to severe cholestatic liver dysfunction. Within the 3.0×10^{14} vg/kg dose level cohort, 8 of 17 subjects (47.1%) experienced 26 SAEs considered related to AT132. In contrast, within the 6 subjects dosed at the 1.0×10^{14} vg/kg dose level, all of whom are ≥ 2 years from AT132 administration, 1 (16.7%) subject experienced 4 AT132-related SAEs, all resolved, and none involved the hepatobiliary system. In addition to a favorable safety profile observed in the subjects treated with 1.0×10^{14} vg/kg, a clinically meaningful benefit continues to be observed in this group at last follow-up. In this group, which had a mean 20.5 hours (SE 2.02) of ventilation per day at baseline ($n = 5$ [83.3%] with invasive ventilation; $n = 1$ [16.7%] with non-invasive ventilation), 5 out of 6 (83.3%) subjects were ventilatory independent at last follow-up (as of data cutoff date 08 July 2020). With respect to gross motor development, at baseline 5 of the 6 subjects did not perform any of the following major motor milestones: sit unassisted for 30 seconds, raise self to standing position, stand alone, or walk alone. At baseline, 1 subject did sit unassisted for 30 seconds but did not perform the remaining motor tasks. At last follow-up following AT132 administration at 1.0×10^{14} vg/kg, 5 out of 6 subjects performed all of these motor tasks, including walking alone. Regarding performance on the Children's Hospital of Philadelphia Infant Test of Neuromuscular Disorders (CHOP INTEND), this 1.0×10^{14} vg/kg group demonstrated a baseline mean score of 37.7 (SE 2.42). At last follow-up, performance had improved to a mean score of 56.5 (3.97).

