3.3 Selection of Study Population

3.3.1 Inclusion Criteria

Subjects must meet all of the following inclusion criteria to be eligible for participation in this study. Subjects assigned to delayed-treatment control will be evaluated to confirm the subject still meets a subset (*) of the inclusion/exclusion criteria before receiving AT132.

1. Subject has a diagnosis of XLMTM resulting from a genetically confirmed mutation in the *MTM1* gene as assessed by a Sponsor-approved testing facility.*
2. Subject is male.*
3. Subject is aged less than 5 years old at dosing.*
4. Subject requires mechanical ventilatory support:
 - Part 1: Subject requires some mechanical ventilatory support (eg, ranging from 24 hours per day fulltime mechanical ventilation, to noninvasive support such as continuous positive airway pressure [CPAP] or bilevel positive airway pressure [BiPAP] during sleeping hours).
 - Part 2: Subject requires invasive mechanical ventilatory support ranging from 20 to 24 hours per day at screening (confirmed by daytime polysomnographic study).
5. Subject requiring invasive mechanical ventilator support is fitted with or willing to be fitted with a cuffed tracheostomy tube for some respiratory assessments.*
6. Subject has ventilator maximum positive end-expiratory pressure (PEEP) < 8 cmH₂O at screening.*
7. Signed informed consent by the parent(s) or legally authorized representative (LAR) (when applicable).*
8. Subject and parent(s)/LAR(s) are willing and able to comply with study visits and study procedures.*
9. UNIQUE to France: Subject's weight is ≥ 4.8 kg.

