5.1.1.6 Vital Signs

Vital signs for this study include blood pressure, heart rate, respiration rate (RR), and temperature. Record whether the subject was on or off of ventilatory support when vital signs are taken.

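### The clinically significant respiratory-rate rows and listing flags in SAP 4.6.2.3 use readings taken on and off the ventilator alike, although the descriptive respiratory-rate table is limited to children off it

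*SAP*

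**What the plan says.** SAP Section 4.6.2.3 sets several rules that bear on respiratory rate (RR):

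- **General summary.** RR is not among the variables named: "Vital signs (systolic blood pressure [SBP], diastolic blood pressure [DBP], temperature, and heart rate) will be summarized".
- **Descriptive RR table.** "A separate table will be provided to summarize respiration rate for participants off ventilator using mean, standard deviation, minimum, maximum and median", broken down by treatment group, age group and visit.
- **PCS tables.** "Tables for potentially clinically significant vital signs will be generated using baseline value and highest/ lowest value obtained during treatment for each participant". Table 6 then gives low and high limits by age band for SBP, DBP, heart rate and RR.
- **Baseline.** "The baseline value will be the last non-missing value taken prior to first dose of study drug".
- **Listing.** Every vital sign is listed, and values beyond the Table 6 limits are flagged.

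The last three rules carry no ventilator condition, and the vital-signs windows in SAP Table 10 add none. Protocol Section 5.1.1.6 instructs sites: "Record whether the subject was on or off of ventilatory support when vital signs are taken". Footnotes to the schedules in Protocol Sections 5.3.1, 5.4, 5.5 and 5.7 repeat the instruction.

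**The concern.** Limiting the descriptive RR table to children off the ventilator makes sense if a supported rate should not be read as the child's own breathing. The PCS rows that follow in the same section drop that limit without comment. A programmer who follows the text would pool all readings.

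RR carries safety information in children who are being weaned. Protocol Section 4.6.3.1 names respiratory weakness as one way neuromuscular abnormality may show itself. Protocol Section 5.1.1.11.1 ends the off-ventilator part of the daytime polysomnogram if the rate rises by 25%. A reader of the PCS table will take a flag as a statement about how the child was breathing. As written, a flag may instead reflect a rate recorded under ventilator support, and the baseline and the post-dose extreme may come from different states.

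**Working it through.** The plan states no figure on this point, so there is none to reproduce. The check compares the rules, then applies them to the Table 6 limits.

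**1. Rules side by side (SAP 4.6.2.3)**

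| Output | RR readings used |
|---|---|
| Descriptive RR table | Off ventilator only |
| PCS baseline | Last non-missing pre-dose value, either status |
| PCS highest and lowest | All readings, either status |
| Listing flags | All readings, either status |

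**2. Does ventilator status change after baseline?** Part 2 entry (Protocol 3.3.1): "Subject requires invasive mechanical ventilatory support ranging from 20 to 24 hours per day at screening". As a share of the day, 20/24 = 83% and 24/24 = 100%. The first six low-dose children averaged 20.5 hours at baseline (Protocol 1.4.2), and 20.5/24 = 85%. Of these same children, "5 out of 6 (83.3%) subjects were ventilatory independent at last follow-up". So a supported baseline followed by unsupported readings is a realistic pattern. These percentages are shares of hours, not of vital-sign readings, and Part 1 also admitted children supported only during sleep.

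**3. Direction within one age band.** Let U and L be the upper and lower limits.

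- Highest value over all readings = max(highest off support, highest on support), which is at least the highest off support.
- Lowest value over all readings = min(lowest off support, lowest on support), which is at most the lowest off support.
- A high flag needs the highest value above U. A low flag needs the lowest value below L.

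Adding on-support readings can therefore create flags but cannot remove them. An enumeration agrees. It took one off-support and one on-support reading, each an integer from 5 to 69 (65 values), in five age bands: 5 × 65 × 65 = 21,125 pairs. Flags were lost in 0 pairs and gained in 8,242. The second count shows direction only and is not an expected frequency.

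**4. Which supported rates would flag?** The documents give no ventilator rates. Assuming recorded on-support rates of 16 to 30 breaths/min (15 integer values):

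| Age band | Table 6 RR limits | Assumed rates that flag |
|---|---|---|
| 1–12 months | below 27, above 45 | 16–26 low (11 of 15) |
| 1–2 years | below 21, above 43 | 16–20 low (5 of 15) |
| 3–5 years | below 18, above 31 | 16–17 low (2 of 15) |
| 6–7 years | below 17, above 25 | 16 low, 26–30 high (6 of 15) |
| 8 years and over | below 12, above 22 | 23–30 high (8 of 15) |

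Only on-support rates outside the limits matter, but one such reading is enough, because a single extreme classifies the child.

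**5. Weight of one child.** At the 8 July 2020 cutoff, Protocol 1.4.2 gives 6 low-dose and 17 high-dose children. One misclassified child moves the PCS percentage by 1/6 = 16.7 or 1/17 = 5.9 points. Three controls were then still undosed, and SAP 1.3 says two were never dosed. If the third received the low dose and nobody else was added, the low-dose group is 7 and the shift is 1/7 = 14.3 points.

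**The case against.** The strongest reply is that this is a drafting gap in one row group of a descriptive table. Much of that stands. SAP Section 2 rules out hypothesis testing. The off-ventilator RR table reports the maximum by age group and visit, and the listing shows every reading. RR is also collected as a ventilator parameter (Protocol 5.1.1.11.5), and those data are listed (SAP 4.4.2.2.7). Serious respiratory events are summarised separately (SAP 4.6.1). SAP Section 4.1 also sends table and listing formats to separate specifications, which are not available here and might contain a filter. The defect is therefore confined to the PCS table and the flags.

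It is also fair to object to simply dropping on-support readings. A high rate despite support may be informative, and many Part 2 children would have little or no off-support baseline.

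Three stronger readings are tempting, and the documents do not support them:

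- **That pooling hides tachypnoea after weaning.** Within an age band it cannot: Table 6 has separate low and high columns, and step 3 of the working shows that no flag is lost. The rule that counts a value only if it is more extreme than baseline is written for laboratory tests (SAP 4.6.2.1), not vital signs, so a high supported baseline does not cancel a later flag. At most, the display looks unchanged from baseline. Masking across age bands requires the extreme to be picked before the age limit is applied. With assumed readings, 40/min on support at 1–12 months (in range) would displace 36/min off support at 3–5 years (above 31). The SAP does not say the extreme is picked first, and off-support readings alone could produce the same problem.
- **That dose groups weaning at different speeds cannot be compared.** The mix of readings may differ, but no dose contrast on RR is planned.
- **That status is recorded in order to restrict this analysis.** The protocol gives no reason for recording it.

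**Conclusion.** The point holds as an internal inconsistency with a modest consequence. Followed as written, SAP 4.6.2.3 lets an on-ventilator rate outside the Table 6 limits make a child PCS, and lets a supported baseline stand beside unsupported extremes. The expected error is over-counting in the PCS table and flags. No efficacy endpoint, test or decision rule is touched.

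The number of children affected is unknown. It depends on actual on-support rates and on how many readings were taken on support. The 16–30 range is an assumption. The conclusion also assumes that the table specifications do not already add a ventilator filter. It still merits a change, because the groups are small enough for one child to be visible in a reported safety percentage and the variable needed is already collected.

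**What to change.** In SAP 4.6.2.3, for RR only:

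- Derive the baseline, the highest and lowest values and the PCS counts separately for off-support and on-support readings, using the recorded on/off status. Make the off-support rows the main ones.
- Add a 'no off-support baseline' category, so that children without one remain visible.
- Apply the age-specific limit to each reading before selecting the extreme.
- Print ventilator status beside each RR value in the listing, so that every flag can be read with it.

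Leave SBP, DBP and heart rate unchanged.

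The cost is a few sentences in the SAP and a by-variable on data already collected. Fewer children will contribute off-support values before weaning, and the table gains a few rows.

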Visit Window (days)	-1	±3	±3	±3	+10	±3	±14	±14	±14	±14	±14	±14
Diary of ventilator dependence ^{a,b}	X											
Ventilator Dependence Questionnaire ^b						X		X	X	X	X	X
Contact subject's caregiver ^c						X						
Physical examination ^d			X		X		X	X	X	X	X	X
Vital signs ^e			X		X		X	X	X	X	X	X
12-Lead ECG ^f			X		X		X	X	X		X	X
ECHO ^f			X				X		X		X ^g	X ^g
Growth parameters			X		X		X	X	X	X	X	X
Tanner stage (puberty assessment)							X		X		X ^{ff}	
Samples for:												
Safety labs (hematology) (central lab) ^{h,i}							X	X	X		X	X
Safety labs (hematology) (local lab) ^{h,i}			X		X							
Safety labs (chemistry) (central lab) ^{h,i,j,k,l}							X	X	X		X	X
Safety labs (chemistry) (local lab) ^{h,i,j,k}		X ^m	X	X ^m	X							
Cytokine panel (central lab) ^{h,n}		As clinically indicated										
Complement panel (central lab) ^{h,o}		As clinically indicated										
Troponin T and/or I (central lab) ^{h,j}							X	X	X		X	X
Troponin T and/or I (local lab) ^{h,j}		X	X	X	X							

Study Phase/Visit	Daily	Weeks 9, 10, 11	Week 12	Weeks 13, 14, 15	Week 16	Weeks 20, 28, 32, 40, 44	Week 24	Week 36	Week 48 or Early Withdrawal	Month 15	Months 18, 24, 30, 36, 42	Months 48, 54, 60
Study Day(s)	NA	63, 70, 77	84	91, 98, 105	112	140, 196, 224, 280, 308	168	252	336	456	548, 730, 913, 1095, 1278	1460, 1643, 1825
Visit Window (days)	-1	±3	±3	±3	+10	±3	±14	±14	±14	±14	±14	±14
Coagulation parameters (central lab) ^{h,i}							X	X	X		X	X
Anti-AAV8 NAb and TAb (central lab)			X		X		X	X	X		X	X
Anti-MTM1 antibody (central lab)			X		X		X	X	X		X	X
IFN-γ ELISpot (PBMCs) (central lab)		As clinically indicated ^p										
HLA typing (central lab) ^q			X ^q						X ^q		X ^q	
Urinalysis (central lab) ^{h,i}							X	X	X		X	X
Urinalysis (local lab) ^{h,i}		X	X		X							
Serum bile acid assay (fasting preferred; central lab)			X				X	X	X	X	X	X
Liver ultrasound ^k			X		X		X	X	X		X	X
Bone age (wrist X-ray) (not applicable for Germany)			X				X		X		X ^{ee}	
Assessment of ventilator parameters			X		X		X		X		X ^{ff}	
MIP, MEP, P0.1, tidal volume ^r			X		X		X		X		X ^{ff}	
Ventilator Weaning and Discontinuation Assessment			X ^s		X ^s		X ^s		X ^s		X ^{s, ff}	
Daytime polysomnogram							X		X ^t			
Secretions management assessment ^u			X		X	X	X	X	X		X	X
Motor milestone assessments ^v			X		X		X	X	X	X	X	X
Bayley-III, motor domain ^v			X		X		X	X	X	X	X ^{ff}	
CHOP INTEND ^{v,w}			X		X		X	X	X		X ^{ff}	
MFM-32 ^v			X		X		X	X	X		X ^{ff}	

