1.2 Study Design

This is a Phase 1/2/3, randomized, open-label, ascending-dose, delayed-treatment concurrent control clinical study to evaluate the safety and efficacy of AAV8-delivered gene therapy in XLMTM participants aged less than 5 years old. Participants will receive a single dose of AT132 and be followed for safety and efficacy for 10 years.

The study consists of 2 parts. Part 1 would establish the optimal dose of AT132. Part 2 would confirm the safety and efficacy of AT132 at the optimal dose level. The following describes how each part was designed and the changes as of protocol v8.

Part 1 (fully dosed as of protocol v8):

A maximum of 3 dose levels of AT132 are planned for evaluation in Part 1 of this study (Figure 1). Four participants will be enrolled in each dose level cohort, including 1 participant in each dose level cohort randomized to control with delayed administration of treatment. The first participant in each dose level cohort will be assigned to receive AT132 and will be treated as a sentinel participant. Subsequent participants in that dose level cohort will be randomized (2:1) to treatment or control with delayed treatment if there are no safety concerns after at least 4 weeks of post-dose data from the sentinel participant is evaluated by the chair of the data monitoring committee (DMC). Dose escalation to the next dose level will be considered after evaluation of at least 4 weeks of data from all participants dosed at the current dose level. Following the dose escalation portion of the study, an optimal dose will be determined in conjunction with the DMC, and control participants will be treated at the optimal dose level.

This study's independent DMC will monitor participant safety and provide recommendations to the Sponsor regarding dose level determination, cohort expansion, and safety and study conduct matters.

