4.6.2.4 Electrocardiograms

ECG variables will be summarized using mean, standard deviation, minimum, maximum and median for each treatment group and overall at each treatment visit and time point, including changes from baseline.

Number and percent of participants with normal, not clinically significant abnormal, and clinically significant abnormal results as assessed by investigator for the 12 lead ECG will be tabulated by treatment group and overall at each treatment visit and time point.

The heart rate, PR, and QTc interval will be summarized using frequency tables for each treatment visit and time point for values of clinical importance using the range criteria below.

Table 7 Potentially Clinically Significant Criteria for ECG

ECG Parameter	Age Group	Pre-specified Level
PR	6 – 11 months	<70, >159
	12 – 23 months	<71 msec, >160 msec
	2 – 3 years	<75 msec, >165 msec
	4 – 5 years	<80 msec, >166 msec
	6 – 7 years	<83 msec, >170 msec
	> 7 years	<85 msec, >182 msec
QTc (Fridericia's)	Any	>450 msec, > 480 msec, >500 msec
QRS	6 – 11 months	< 40, > 101 milliseconds
	12 – 23 months	< 40, > 105 msec
	2 – 3 years	< 40, > 115 msec
	4 – 5 years	< 41, > 125 msec
	6 – 7 years	< 52, > 118 msec
	> 7 years	< 60, > 122 msec
Heart rate	6 – 11 months	< 65, 188 beats/min
	12 – 23 months	< 56, > 184 beats/min
	2 – 3 years	< 46, > 168 beats/min
	4 – 5 years	< 38, > 146 beats/min
	6 – 7 years	< 40, > 128 beats/min
	> 7 years	< 30, > 122 beats/min

The QTc interval will also be summarized by the frequencies of participants with a change from baseline of clinical importance using the criteria identified below. These summaries will be provided for each treatment visit and time point.

Table 8 Potentially Clinically Significant Criteria for QTc

Variable	Change from Baseline
QTc Interval (msec)	> 30
	> 60

Number and percent of participants whose 12 lead ECG reading changed from normal at baseline to abnormal will be tabulated by treatment group at each treatment visit and time point.

Listings will present ECG data, such as overall interpretation of ECGs, assessments of heart rate (HR), and intervals of PR, QRS, QT, QTc (with method), as well as other specifications. The listing will flag any results that are outside the levels provided in the table above.

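### The table of potentially clinically significant vital signs tests only each child's highest and lowest value against limits that change with age, so it can undercount affected children

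*SAP*

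**What the plan says.** SAP 4.6.2.3 (Vital Signs) says that the PCS tables are produced for each treatment group "using baseline value and highest/ lowest value obtained during treatment for each participant". Table 6, directly below, gives low and high limits for systolic and diastolic blood pressure, heart rate and respiratory rate in five age bands, from 1-12 months to 8 years and over. The section does not say whether the extremes are taken within an age band, by visit or by period. Nor does it say whether age at dosing or age at measurement selects the limit.

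The same section adds: "The listing will flag any vital signs that exceed the levels provided in the table above".

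Protocol 3.3.1 requires that the "Subject is aged less than 5 years old at dosing". SAP 1.2 says: "Participants will receive a single dose of AT132 and be followed for safety and efficacy for 10 years". In the treated-subject schedule (Protocol 5.5), the vital-signs row runs to the last column, "Months 48, 54, 60". The schedule for Months 72 to 120 (Protocol 5.6) has no vital-signs row.

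The ECG limits in SAP 4.6.2.4 are also mostly age-banded. There the plan is different: heart rate, PR and QTc "will be summarized using frequency tables for each treatment visit and time point for values of clinical importance using the range criteria below".

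**The concern.** A raw maximum or minimum identifies the worst value only when the limit is fixed. Here the limits move as the child grows. The highest heart rate will often come from the youngest age, where high rates are normal, and the lowest blood pressure likewise. If that extreme is in range for its age, no other value is tested, and a child with a value that is abnormal for age is left out.

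The error runs in one direction. A child whose extreme is out of range for its age is rightly counted, so the rule can undercount but cannot overcount. At stake is a safety table that reports too few affected children and does not reconcile with the listing in the same report. The phrase *during treatment* makes this harder to judge, because one infusion has no treatment period and the SAP does not define one for this table.

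**Working it through.** The plan gives no figure to reproduce. The check uses the Table 6 limits, the visit schedule and a simulation.

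**1. Limits (SAP Table 6, low/high).**

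| | 1-12 months | 1-2 years | 3-5 years | 6-7 years | 8 years and over |
|---|---|---|---|---|---|
| Heart rate, bpm | 111/182 | 108/180 | 88/152 | 75/118 | 60/100 |
| SBP, mmHg | 72/104 | 86/106 | 89/112 | 97/115 | 102/131 |
| DBP, mmHg | 37/56 | 42/63 | 46/72 | 57/76 | 64/83 |
| Respiratory rate, per min | 27/45 | 21/43 | 18/31 | 17/25 | 12/22 |

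Both limits change between every pair of adjacent bands, for all four signs.

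**2. Hypothetical children whom the rule leaves out.**
- Heart rate, high: 170 at age 1 (limit 180, in range) and 160 at age 4 (limit 152, out of range). The maximum is 170, so the child is not counted.
- Heart rate, low: 100 at 18 months (limit 108, out of range) and 95 at age 5 (limit 88, in range). The minimum is 95, so not counted.
- SBP, low: 88 at 18 months (limit 86, in range) and 90 at age 6 (limit 97, out of range). The minimum is 88, so not counted.
- SBP, high: 110 at 20 months (limit 106, out of range) and 111 at age 4 (limit 112, in range). The maximum is 111, so not counted.

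**3. How many children change band.** The bands are read in completed years, so the boundaries lie at ages 1, 3, 6 and 8. Followed for five years, a child dosed before age 1 reaches the 3-5 band, one dosed at 1-2 years reaches 6-7, and one dosed at 3-4 years reaches 8 and over. Each spans three bands, apart from a day or so at the edges. Over shorter periods fewer change band. Assume age at dosing uniform from 3 months to 5 years, a width of 4.75 years:
- Week 24: 168/365.25 = 0.46 years. The boundaries at 1 and 3 can be crossed: 2 × 0.46/4.75 = about 19%.
- Week 48: 336/365.25 = 0.92 years. Boundary 1 is crossed by those dosed from 0.25 to 1 year (0.75) and boundary 3 by a further 0.92: (0.75 + 0.92)/4.75 = about 35%.

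**4. Share missed (illustrative simulation).** Protocol 5.4 and 5.5 schedule vital signs on 21 post-dose days to Month 60 (7 through Week 8, then 14). With L and U the limits for age on the day, each value is (L + U)/2 + e × (U − L)/(2z), where e is standard normal and z is 2 to 3, so that the limits lie z SD from the centre. Then

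missed share = 1 − P(raw extreme is out of range for its age) / P(any value is out of range for its age).

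| Period | Independent values, range over signs and directions | Within-child correlation 0.5, upper end |
|---|---|---|
| Through Week 24 | about 0-6% | about 9% |
| Through Week 48 | about 1-9% | about 21% |
| Through Month 60 | roughly 24-58% | about 76% |

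The ends of these ranges move by up to about three points between runs. By sign, through Month 60 with independent values (here with age at dosing from 0.1 years and limits at 1.96 to 3.0 SD), the missed shares are:

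| | High | Low |
|---|---|---|
| Heart rate | 29-35% | 49-57% |
| SBP | 47-53% | 25-28% |
| DBP | 49-55% | 24-27% |
| Respiratory rate | 32-37% | 39-49% |

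**5. Effect on reported counts.** If a share m is missed, correcting the rule multiplies the count by 1/(1 − m). For m = 24% that is 1/0.76 = 1.32, and for m = 58% it is 1/0.42 = 2.38. For m = 6% it is 1/0.94 = 1.06.

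**The case against.** **The period may be short.** SAP 4.6.2.2 uses a 24-week investigational period for its liver threshold counts, and a reader could carry that over. The missed share would then be a few percent. This stands: the large figures hold only if *during treatment* means all scheduled follow-up. A 24-week reading would, however, leave most of the scheduled follow-up out of the table, and the rows for 6-7 years and for 8 years and over would be empty, because a child dosed before age 5 is under 6 at Week 24.

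**The table shells may resolve it.** SAP 4.1 refers formats to the TLF specifications, which are not available here. Table 6 is laid out by age group, and 4.6.2.3 already summarises respiratory rate off ventilator by age group. Extremes taken within age band would remove the problem. The SAP neither says nor excludes this, but its stated rule is one highest and one lowest value per participant.

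**Nothing is lost from the report.** The listing flags every value, and SBP, DBP and heart rate are summarised by visit with minimum and maximum. ECG heart rate is tabulated by visit against age-banded limits. Protocol 4.6.1.1 rests myocarditis surveillance mainly on clinical assessment and troponin. A reader might infer that abnormal values disappear. They do not; a child can drop out of one count.

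**Dose comparison.** A reader might also infer that low-dose and high-dose rates cannot be compared. The documents do not support this. They show no difference between the groups in age at dosing or length of follow-up that would make the undercount differ, and SAP sections 2 and 4.1 make all summaries descriptive.

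**The simulation is simple.** It takes one value per day, although Days 1 to 3 have repeated readings, and it ignores ventilation, which constrains respiratory rate. The figures show the order of size only.

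**Conclusion.** The concern holds as a fault in one table's rule. Testing one raw maximum and one raw minimum per child against limits that change with age can leave out a child with an out-of-range value, and the count can then disagree with the listing. The examples follow from Table 6 and need no assumption beyond using age at measurement. That reading is the sensible one, since no child is dosed at an age that would use the two oldest bands.

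The size is uncertain because the period is undefined: small over 24 or 48 weeks and substantial over five years. It rests on assumed ages, distributions and correlation. The primary analysis is not affected. The change is worth making because the table is wrong in principle and the correction is cheap.

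**What to change.** In SAP 4.6.2.3, replace the highest/lowest rule. Classify every post-dose value against the Table 6 band for the child's age on the day of measurement, and count a participant once for each criterion if any value meets it. Replace *during treatment* with *after AT132 administration*, tabulated by the four periods in SAP 4.6.1 (through Week 24, after Week 24 through Week 48, after Week 48 to end of study, and overall). Splitting by period alone would not be enough, because the last period still spans several age bands.

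The cost is a small text change and a small programming change, since the listing already needs the same flag for each value. Reported PCS counts may rise, possibly noticeably over long follow-up.
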